#### **6.4.3 Management of Specific Adverse Events or Adverse Drug Reactions**

No specific measures are proposed for this trial. Standard medical care will be provided at the trial site for all AEs occurring during the trial.

##### **6.4.3.1 Management of Latent Tuberculosis Infection Diagnosed During the Study**

It is highly recommended to adhere to national/institutional guidelines to manage and treat subjects diagnosed as LTBI during the study.

Patients with a positive QFT at screening will be ineligible for the trial. Investigators may treat them per local/national guidance for LTBI outside of the study.

If a patient with a negative QFT during screening develops a positive QFT during the trial (ie, at Week 24), treatment with IMP should be stopped and an early termination visit completed. Such patients continue safety/immunogenicity visits (see [Table 1](#) for schedule of assessments). The patient will return for a safety follow-up visit 4 weeks after the last dose of IMP and an additional safety evaluation visit 4 months after the last dose of IMP.

During this 4-week safety follow-up period no excluded treatment for RA (as defined in the protocol) should be administered. Patients will return for an additional safety follow-up visit 4 months after the last dose of IMP. Treatment for RA from the 4-week safety follow-up visit to the 4-month visit will be at the discretion of the Investigator following institutional standard of care. The 4-week and 4-month safety follow-up visits will not be duplicated if either of these visits falls within 2 weeks of an otherwise scheduled visit. If the 4-week and 4-month safety follow-up visits since the last IMP are completed within the 52-week visit schedule, these will not be repeated thereafter.

Patients who were QFT-negative at randomization but subsequently become QFT-positive at Week 24 should, at the safety follow-up visit (4 weeks after the last IMP administration), be referred by the Investigator for a consultation with an infectious disease specialist/pulmonologist as necessary in order to assess whether TB re-activation occurred during the trial.

Patients who were QFT-negative at randomization and at Week 24 but subsequently became QFT-positive at Week 52 should be referred by the Investigator for a consultation with an

infectious disease specialist/pulmonologist as necessary in order to assess whether TB re-activation occurred during the trial.

If a patient develops active TB disease during the trial, treatment with IMP should be stopped immediately.

## **6.5 Packaging and Labeling of the Investigational Medicinal Product**

MSB11022-**CCI** drug product will be manufactured by the Sponsor, and Humira® will be sourced by the Sponsor from a wholesaler. Packaging and labeling will be in accordance with applicable local regulatory requirements and applicable Good Manufacturing Practice guidelines.

Packaging of all IMPs for the trial will be done by the Sponsor's contract manufacturing organization, **PPD**.

MSB11022-**CCI** and Humira® will be provided in single-use prefilled syringes. Each prefilled syringe with plunger rod assembly will be packed in a carton box that will be closed with a tamper-evident seal. The IMPs will be packaged in a blinded fashion, or the sponsor will put in place a process to avoid any bias in the blinding. Full re-traceability according to current Good Manufacturing Practice guidelines will be provided based on the unique medication number on the labels together with packaging documentation.

The IMPs will be shipped and stored under controlled conditions according to the storage requirements (2°C to 8°C/36°F to 46°F).

The IWRS will support the logistics of the IMP.

## **6.6 Preparation, Handling, and Storage of the Investigational Medicinal Product**

Handling instructions will be provided in a prepared handling guideline for MSB11022-**CCI** and in the Summary of Product Characteristics document for Humira®.

All IMPs must be stored in a secure area with limited access under controlled conditions at 2°C to 8°C/36°F to 46°F and protected from light. The IMP must not be frozen, and rough shaking of the solution must be avoided.

Patients or family members/caregivers who receive appropriate training will be permitted to administer medication in this trial. To ensure compliance with recommended storage conditions, all patients will be provided with cooler bags to transport the IMP home. Patients will be provided with instructions on proper storage, including instructions to store their trial treatment under refrigeration at 2°C to 8°C (36°F to 46°F) and not to leave their medication unattended or in a place that might get too hot, eg, inside a car. Patients should have access to refrigeration to store the IMP. Patients will also receive sharps containers and handling instructions.

The IMPs will be supplied in single-use prefilled syringes and no further preparation is required. The syringes must be kept in the original outer packaging until administration.

The preparation should be carefully inspected before injection (it should be a homogenous looking clear solution, free of visible particles).

In the event of a temperature deviation at the clinical site, the site must contact the clinical research associate without delay for further evaluation and assessment by the designated quality assurance personnel at Merck KGaA or their delegate. The medication with the temperature excursion should still be stored at the required temperature but quarantined during the investigations and must be appropriately labeled as “quarantine storage”.

Additional details on the instructions for handling and storage will be described in the drug administration instructions and provided to patients as required for administration at home.

The IMP should not be administered after the date of expiration indicated on the product packaging.

## 6.7 Investigational Medicinal Product Accountability

The Investigator (or designee) is responsible for ensuring IMP accountability, including reconciliation of drugs and maintenance of records.

- Upon receipt of IMP, the responsible person will check for accurate delivery and acknowledge receipt by signing or initialing and dating the appropriate documentation and storing it in the Pharmacy File as well as entering it into the IWRS.
- IMP dispensing, which will be triggered by the IWRS, will be recorded on the appropriate drug accountability forms so that accurate records will be available for verification at each monitoring visit.
- Trial site IMP accountability records will include the following:
  - Confirmation of IMP receipt, in good condition and in the defined temperature range.
  - The inventory of IMP provided for the clinical trial.
  - The use of each dose by each patient.
  - The disposition (including return, if applicable) of any unused IMP.
  - Dates, quantities, batch numbers, kit/syringe numbers, use-by dates, and the individual patient trial numbers.

The Investigator site should maintain records, which adequately document that patients were provided the doses specified in this protocol, and all IMPs provided were fully reconciled.

The IWRS should only be contacted after all scheduled assessments are completed and the patient's eligibility to remain in the trial is confirmed. Unused IMP must not be discarded or used for any purpose other than the present trial. No IMP that is dispensed to a patient may be dispensed to a different patient.

The monitor will periodically collect the IMP accountability forms and will check all returns (both unused and used containers) before authorizing their destruction by the trial site. The preferred option is always to destroy used/unused medication at the trial site. Only in exceptional cases can the medication be returned to the Sponsor or designee for destruction.

## 6.8 Assessment of Investigational Medicinal Product Compliance

The IMP will be administered at the site on the trial visit days defined in [Table 1](#). All other dosing will be done by the patient or patient's caregiver at home throughout the rest of the trial. Patients will be asked to record the date and time dispensed, date and time of dosing, location of administration, and injection site reaction (yes/no) in a patient diary. Diaries will be collected and reviewed at the trial visits specified in [Table 1](#).

Patients will be instructed to bring all IMP, including the used packaging, to each trial visit to allow for the assessment of compliance with trial treatment. Prior to discharge from each scheduled visit, patients will be given sufficient IMP for at-home dosing until the next scheduled visit.

## 6.9 Blinding

This trial will be double-blinded. Blinding will be maintained throughout the trial duration, unless an emergency unblinding is necessary. In the event of a change in the reference product (eg, introduction in the market of the new 0.4 mL Humira® formulation) prior to the completion of this study, the sponsor will put in place a process to avoid any bias in the blinding. Randomization data will be kept strictly confidential, accessible only to authorized staff, until the time of unblinding. The trial blind may be broken for an individual only if knowledge of the IMP is essential for clinical management of an incurred SAE; however, unblinding is discouraged as knowledge of the treatment received has limited influence on the treatment of AEs. If the Investigator breaks the blind, he must contact the medical monitor immediately, and no later than 24 hours after performing the unblinding, without sharing any treatment assignment information. The Investigator must promptly explain the reason for any unblinding of an IMP to the Sponsor without revealing the result to any Sponsor employee except the designated Drug Safety representative. The Investigator must record the date of unblinding and the reason in the CRF. Under certain circumstances, Drug Safety may be required to unblind the treatment assignment for an individual patient following an SAE or other serious event; for example, if an expedited regulatory report is required. The CRO Medical Monitor will not break the blind.

All breaks of the trial blind must be adequately documented.

## 6.10 Emergency Unblinding

The trial blind may be broken for an individual only if knowledge of the IMP assignment is essential for clinical management of the patient. The Investigator must promptly explain the reason for any unblinding of an IMP to the Sponsor without revealing the result to any Sponsor employee except the designated Drug Safety representative (using the Emergency Unblinding Notification Form). The Investigator must record the date of unblinding and the reason in the CRF. Contact

information for breaking the blind in an emergency is given on the patient emergency card provided to each patient (see Section 9.4).

Under certain circumstances, Drug Safety may be required to unblind the treatment assignment for an individual patient following a serious adverse event (SAE) or other serious event; for example, if an expedited regulatory report is required. See Section 7.4 for further details on expedited reporting and SAEs.

## 6.11 Treatment of Overdose

An overdose is defined as any dose greater than the highest daily dose included in a clinical trial protocol. In the event of an overdose, patients should receive appropriate supportive medical care and be followed until resolution/stabilization of any clinical issues.

Even if it does not meet other criteria for an SAE, any overdose must be recorded in the trial medication section of the CRF and reported to Drug Safety in an expedited manner using the appropriate reporting form, and following the procedure in Section 7.4.

## 6.12 Medical Care of Patients after End of Trial

The Sponsor will not provide any additional care to patients after they leave the trial. After patients leave the trial, medical care will be at the discretion of the Investigator following institutional standard of care.

# 7 Trial Procedures and Assessments

## 7.1 Schedule of Assessments

Assessments during the trial will be performed according to Table 1. Patient reported outcome questionnaires must be performed prior to any other assessments at all visits. For volumes of blood collected, see Appendix C.

Prior to performing any trial assessments that are not part of routine medical care for the patient, the Investigator will obtain written informed consent as described in Section 9.2.

### 7.1.1 Screening Procedures and Assessments

The screening procedures will be completed within 28 to 3 days prior to drug administration.

The IWRS must be notified within 5 days of patients who fail screening. The following information, at a minimum, should be collected in the eCRF for patients who failed screening: informed consent, inclusion/exclusion criteria, basic demographics, reason for screen failure, AEs from the date of informed consent until patient is considered to have failed screening by the Investigator, and the Investigator's signature.

During screening, a serum  $\beta$ -human chorionic gonadotropin ( $\beta$ -hCG) pregnancy test will be performed for females of childbearing potential, and blood HIV, hepatitis B virus, and hepatitis C

virus tests will be performed for all screening patients as these conditions are trial entry exclusion criteria (see Section 5.3.2). Testing for TB will be performed as described in the exclusion criteria.

Patients who do not meet the inclusion/exclusion criteria within the specified time limits (ie, 28 days to 3 days prior to drug administration) and fail screening may undergo re-screening once, if approved by the Medical Monitor. If the patient is re-screened, the patient will receive a new patient identification number and will be asked to sign a new ICF. Such re-screened patients will undergo complete screening assessments.

Patients with test results that do not meet the inclusion/exclusion criteria may have testing repeated once only if the results are thought to represent a laboratory error or a reversible or clinically insignificant intermittent condition. If testing is repeated for such patients, all screening tests will need to be repeated except for the chest X-ray, ECG, TB test, HIV, and hepatitis testing, which may be repeated separately from the other tests as necessary. The Medical Monitor may also give permission for tests to be repeated separate from other tests as necessary. If inclusion/exclusion criteria are not met based on the results of the repeated tests, the patient should be considered a screen failure and not be enrolled in the trial. Repeat tests should be conducted and results available within 28 to 3 days prior to baseline.

### 7.1.2 Baseline Assessments and Treatment Period

During the 52-week period, patients will be asked to visit the trial site at the visits indicated in the Schedule of Assessments (Table 1). Except for the Day 1/Week 0 (baseline) visit, a time window of up to 2 days before or after ( $\pm 2$  days) the scheduled day will be permitted for all trial visits during the treatment period.

Demographics, medical history, and inclusion/exclusion criteria will be reviewed to ensure that patients remain eligible for the trial.

An Emergency Medical Support card will be handed out on Day 1/Week 0 (baseline).

The IWRS will be contacted on Day 1/Week 0 (baseline) for patient randomization after all eligibility criteria have been confirmed. Patients will be randomized to receive either 40 mg MSB11022-CCI or 40 mg Humira® every other week starting on Day 1/Week 0 (baseline) and continuing up to and including Week 48. If the IMP is well tolerated as per medical judgment, and reflects the expected safety profile during these visits, the remainder of the patients will be dosed. The IMP is administered at the trial site for the first 3 doses; at Weeks 0, and 2, the patient or a caregiver will be trained for self-injection/injection and at Week 4, the patient will self-inject. Patients will be monitored for 1 hour following IMP administration on Day 1/Week 0, Week 2, and Week 4. Patients or their caregivers will administer the IMP for all subsequent doses and record the dosing date and time in a diary.

Patients who achieve less than 20% improvement in both swollen and tender joint counts at Week 24 (non-responders) will be discontinued from IMP and must immediately perform the assessments listed for the early termination visit and return for the safety follow-up visit 4 weeks after the last dose of IMP in addition to a safety follow-up visit 4 months after the last dose of IMP.

Patients who discontinue from the study medication (but remain in the trial and continue safety/immunogenicity visits) before the Week 52 visit will immediately complete an Early Termination visit and return for a Safety/Follow-up visit 4 weeks after the last dose of IMP. During this 4-week Safety Follow-up period, no excluded treatment for RA (as defined in this protocol) should be administered. Patients will return for an additional safety evaluation 4 months after the last dose of IMP. Treatment for RA from the 4-week Safety Follow-up visit to the 4-month Safety Evaluation visit will be at the discretion of the Investigator following institutional standard of care. The 4-week and 4-month Safety Follow-up visits will not be duplicated if either of these visits falls within 2 weeks of an otherwise scheduled visit. If the 4-week and 4-month Safety Follow-up visits since last IMP are completed within the 52 week visit schedule, these will not be repeated thereafter.

### 7.1.3 Early Termination Visit

Patients who discontinue the trial for any reason other than consent withdrawal before the Week 52 visit must undergo an early termination visit immediately upon discontinuation.

Assessments scheduled during the early termination visit are presented in [Table 1](#).

### 7.1.4 Safety Follow-up Period

All patients will have a subsequent safety follow-up visit scheduled 4 weeks ( $\pm 1$  week) after the last dose of IMP, in addition to a safety follow-up visit 4 months ( $\pm 1$  week) after the last dose of IMP. The assessment for these visits are presented in [Table 1](#).

## 7.2 Demographic and Other Baseline Characteristics

### 7.2.1 Demographic Data

At screening, the following demographic data will be collected: date of birth, sex (gender), race, and ethnicity.

### 7.2.2 Medical History

A complete medical history of each patient will be collected and documented during screening, which will include, but may not be limited to, the following:

- Past and concomitant diseases (nonmalignant and malignant) and treatments
- All medications (including herbal medications) taken and procedures carried out within 28 days prior to screening. The site should document any biologic ever used by the patient.

For trial entry, all of the patients must fulfill all inclusion criteria described in [Section 5.3.1](#), and none of the patients should fulfill any exclusion criterion from the list described in [Section 5.3.2](#). Significant findings that are observed after the patients signs the ICF and that meet the definition of an AE must be recorded in the AE section of the CRF.

## 7.2.3 **Tuberculosis Status**

Assessment of TB status will be required before randomization.

### 7.2.3.1 **Imaging**

Bi-directional chest X-ray will be used to determine eligibility. If the QFT test is negative, a bi-directional chest X-ray, chest high-resolution CT, or chest MRI obtained within 12 weeks prior to randomization will be acceptable. If needed to rule out active TB, chest high-resolution CT or chest MRI could be subsequently performed.

If imaging evaluated by a qualified physician shows evidence of ongoing infectious disease, signs of active TB, or evidence of any malignant process, the patient will not be eligible to enter the trial.

### 7.2.3.2 **QuantiFERON-TB Gold In-Tube assay**

A QFT will be performed to assess the TB status during screening for all patients. Additional tests will be performed according to the Schedule of Assessments for patients whose previous QFT was negative. The QFT test will be supplied and analyzed by the central laboratory. Details on the collection, shipment of samples and reporting of results by the central laboratory are provided in the Laboratory Manual. Refer to Section [6.4.3.1](#) for guidance on treatment for patients with TB.

## 7.2.4 **Immunogenicity**

A blood sample will be collected at screening for assay validation purposes only, no results will be reported and at baseline (on Day 1/Week 0 before IMP administration).

## 7.2.5 **Other Baseline Assessments**

All other baseline measurements, such as vital signs, a complete physical examination, clinical laboratory parameters, chest X-ray, and 12-lead ECG, will be assessed. Screening assessments will be rechecked to confirm eligibility for the trial. If the ECG findings are clinically relevant and would prevent the patient from participating in the trial, the patient should not receive IMP.

## 7.3 **Efficacy Assessments**

The following tests and procedures have been selected to evaluate the efficacy of MSB11022-**CCI** and describe clinical improvement in patients with RA and will be performed according to the Schedule of Assessments ([Table 1](#)).

### 7.3.1 **Disease Activity Assessments**

Assessments for RA disease activity will include ACR response criteria, DAS28-ESR, CDAI, and SDAI, which are described below.

### 7.3.1.1

### American College of Rheumatology Response Rates

The individual components that make up the ACR Core Set of measures for RA are described below. Relief of signs and symptoms will be assessed using the ACR Responder Index, a composite of clinical, laboratory, and functional measures in RA. The ACR responses are presented as the minimal numerical improvement from baseline in multiple disease assessment criteria. The response criteria is based on the 68-joint tender/painful joint count, the 66-joint swollen joint count, and the CRP level.

#### ACR Core Set

##### a. Tender Joint Count (TJC)

For ACR measures, the number of tender and painful joints will be determined by examination of 68 joints (34 joints on each side of the patient's body; see [Appendix D](#)). The 68 joints to be assessed and classified as tender or not tender include: 2 temporomandibular joints, 2 sternoclavicular joints, 2 acromioclavicular joints, 2 shoulder joints, 2 elbow joints, 2 wrist joints, 10 metacarpophalangeal joints, 2 interphalangeal joints of the thumb, 8 proximal interphalangeal joints of the hands, 8 distal interphalangeal joints of the hands, 2 hip joints, 2 knee joints, 2 ankle joints, 2 tarsus, 10 metatarsophalangeal joints of the feet, 2 great toes (first proximal interphalangeal joint of the feet), and 8 proximal interphalangeal joints of the feet.

Joints will be assessed for tenderness by pressure and joint manipulation on physical examination. The patient will be asked for pain sensations on these manipulations and watched for spontaneous pain reactions. Any positive response on pressure, movement, or both will then be translated into a single tender-versus-nontender dichotomy. Joint assessments of 1 particular patient should be performed (if at all possible) by the same assessor throughout the trial to minimize inter-observer variation.

Missing, replaced, ankylosed, or arthrodesed joints will be identified by the Investigator at the screening visit and will be excluded from evaluation during the trial. The locations (or a listing) of surgical procedures should be documented in the patient's source documents/CRF pages.

##### b. Swollen Joint Count (SJC)

For ACR measures, the number of swollen joints will be determined by examination of 66 joints (33 joints on each side of the patient's body). The 66 joints to be assessed and classified as swollen or not swollen include: 2 temporomandibular joints, 2 sternoclavicular joints, 2 acromioclavicular joints, 2 shoulder joints, 2 elbow joints, 2 wrist joints, 10 metacarpophalangeal joints, 2 interphalangeal joints of the thumb, 8 proximal interphalangeal joints of the hands, 8 distal interphalangeal joints of the hands, 2 knee joints, 2 ankle joints, 2 tarsus, 10 metatarsophalangeal joints of the feet, 2 great toes (first proximal interphalangeal joint of the feet), and 8 proximal interphalangeal joints of the feet.

Joints will be classified as either swollen or not swollen. Swelling is defined as palpable fluctuating synovitis of the joint. Swelling secondary to osteoarthritis will be assessed as not swollen, unless

there is unmistakable fluctuation. Joint assessments of 1 particular patient should be performed by the same assessor (if at all possible) throughout the trial to minimize inter-observer variation.

Missing, replaced, ankylosed, or arthrodesed joints will be identified by the Investigator at the screening visit and will be excluded from evaluation during the trial. The locations (or a listing) of surgical procedures should be documented in the patient's source documents/CRF pages.

Any joint which will have received an intra-articular steroid injection will be excluded by the joint count and will be documented as "not done" (ND) for the following 12 weeks. After this time the joint may be assessed again.

c. CRP

CRP will be the ACR Core Set measure of acute phase reactant. It will be measured at the central laboratory to help assess the effect of MSB11022-**CCI** or Humira® on the patient's RA.

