### 5.3.1 Inclusion Criteria

1. Must voluntarily give written informed consent. Patients must read and fully understand the Informed Consent Form (ICF) and the requirements of the trial and must be willing to comply with all trial visits and assessments.
2. Moderately to severely active diagnosis of RA with disease duration of at least 6 months from confirmed diagnosis, as defined by the 2010 revised ACR/EULAR 2010 criteria or the 1987 ARA criteria (Criteria of American Rheumatology Association) (present or past).
3. Have moderately to severely active disease despite MTX therapy defined as:
  - a.  $\geq 6$  swollen joints and  $\geq 6$  tender joints (from the 66/68 joint count system) at screening and randomization.
  - b. Either ESR (Westergren)  $\geq 28$  mm/h or serum CRP  $\geq 1.0$  mg/dL at screening.
4. Must have been treated with MTX for a total of at least 12 weeks prior to baseline and must have been on both: a stable route of administration (oral or parenteral) and stable dose of MTX (10 to 25 mg/week) for at least 4 weeks prior to screening.
5. Age 18 and older.
6. Must be adalimumab naïve and must not have received a non-marketed experimental biological agent for their RA in the past, or any biological agent not belonging to the class of TNF inhibitors. Patients who have received no more than 1 TNF inhibitor (either originator or investigational biosimilar candidate that underwent comparison with EU or US reference compounds) other than adalimumab are allowed to participate in the trial.
7. Must have discontinued infliximab (either originator or investigational or approved biosimilar), certolizumab pegol (either originator or investigational or approved biosimilar) or golimumab (either originator or investigational or approved biosimilar) 8 weeks prior to screening, or etanercept (either originator or investigational or approved biosimilar) 4 weeks prior screening.
8. A female patient is eligible to participate if she is not pregnant (see [Appendix A](#)), not breast feeding, and at least one of the following conditions applies:
  - a. Not a woman of childbearing potential (WOCBP) as defined in [Appendix A](#)

OR

- b. A WOCBP who agrees to use a highly effective contraception (ie, methods with a failure rate of less than 1% per year) as detailed in [Appendix A](#) of this protocol 3 months before the start of the first dose of the IMP, during the treatment period, and for at least 5 months after the last dose of the IMP.

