#### **6.4.2 Prohibited Medicines**

The use of prohibited medications will require the patient to be withdrawn from the IMP.

All biological and non-biological DMARDs other than MTX and hydroxychloroquine or chloroquine are prohibited during the study and must be discontinued prior to the initiation of IMP in accordance with specifications as per the inclusion and exclusion criteria.

High potency opioid analgesics (eg, methadone, hydromorphone, oxycodone, fentanyl, or morphine) as per the inclusion and exclusion criteria.

**Intravenous, intramuscular or intra-articular corticosteroids:** Intravenous or intramuscular corticosteroids are not permitted during the study. Intra-articular corticosteroids are not permitted within 6 weeks prior to baseline. Injection of intraarticular steroids while on blinded study medication is discouraged, but may be used in a limited fashion. No more than 1 joint per 24-week period may be injected during the core period of the study and should not be given 8 weeks or less before the Week 24 visit. No single injection should exceed 40 mg of triamcinolone (or equivalent).

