15.2 Secondary Endpoint Analyses

15.2.1 Key Secondary Endpoint Analyses

The key secondary endpoint is ACR20 at Week 12.

The ACR20 is a key efficacy measure for which a subject must have at least 20% improvement from baseline in the following ACR Core Set values:

• TJC (68 joint count) and

- SJC (66 joint count) and
- An improvement of at least 20% from baseline in at least three of the following five assessments:
 - Patient's Global Assessment of Disease Activity on a visual analog scale (VAS)
 - Patient's Assessment of Arthritis Pain
 - Patient's Assessment of Physical Function as measured by the HAQ-DI
 - Physician's Global Assessment of Disease Activity
 - Acute phase reactant as measured by CRP.

The proportion of subjects with an ACR20 response at Week 12 in the two treatment arms will be reported along with Exact 95% CIs, calculated with the Clopper-Pearson method. The 95% CI for the difference between treatment arms in the proportion of subjects with an ACR20 response at Week 12, calculated with the Newcombe method, will also be presented.

The analyses will be carried out on both the ITT and the PP analysis sets.

Proportions for the two treatment arms will also be presented broken down by the subgroups for the ITT analysis set as described in Section 10.2.6.

Missing data will be handled as described in Section 11.4.1.

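### An injected joint leaves the swollen joint count for 12 weeks with no matching rule for baseline, which can tip borderline joint-count responders; the effect is probably small

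*Protocol*

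**What the plan says.** Protocol 7.3.1.1, under Swollen Joint Count, states: "Any joint which will have received an intra-articular steroid injection will be excluded by the joint count". The joint is recorded as not done "for the following 12 weeks. After this time the joint may be assessed again". The Tender Joint Count text has no such rule.

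Joints that cannot be assessed from the outset are handled differently. In both counts, "Missing, replaced, ankylosed, or arthrodesed joints will be identified by the Investigator at the screening visit and will be excluded from evaluation" for the whole trial, so baseline and follow-up cover the same joints.

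Protocol 6.4.2 discourages intra-articular steroid during blinded treatment but allows it within limits: "No more than 1 joint per 24-week period may be injected during the core period of the study", and an injection "should not be given 8 weeks or less before the Week 24 visit".

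Response is measured against baseline. SAP 15.2.1 says "The ACR20 is a key efficacy measure for which a subject must have at least 20% improvement from baseline" in both joint counts and in three of five other measures. Protocol 7.3.1.1 describes ACR response as numerical improvement, and SAP 11.7 fixes baseline as a single value taken up to first dose. SAP 11.4.1 covers a missing ACR20 result, not a missing joint within a count. SAP 15.3.1.2 gives item-level missing-data rules for HAQ-DI; the joint counts have none.

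**The concern.** A joint chosen for injection is usually an active one. If it was swollen at baseline and is then left out of the follow-up count, the count falls by one although the joint did not respond to study drug. The swollen and tender counts also diverge: the same joint is left out of one and, after the steroid, still assessed in the other.

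The silence leaves the programmer several choices. The joint can be treated as not swollen, dropped from both visits, prorated, or allowed to make the whole count missing. In the last case ACR20 itself is missing: the patient becomes a non-responder in the imputed analysis of SAP 11.4.1, or leaves the denominator under SAP 11.1. One patient could therefore be a responder, a non-responder or excluded.

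At stake are ACR20 at Week 12 (the key secondary endpoint), ACR50, ACR70 and Boolean remission. The swollen and tender counts also feed the Week 24 rule on continuing study drug.

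**Working it through.** The plan gives no figure on this point, so there is none to reproduce.

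**Inputs from the documents**
- Minimum baseline swollen count: 6 (Protocol 5.3.1, criterion 3).
- Thresholds: 20%, 50% and 70% (SAP 15.2.1 and 15.2.2.2).
- One injected joint per 24-week period (Protocol 6.4.2), excluded for 12 weeks (Protocol 7.3.1.1).
- Boolean limit: at most 1 swollen joint (SAP 15.2.2.7).
- 130 patients per arm (SAP 7.1).

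**Assumptions not in the documents**
- The injected joint was swollen at baseline and just before the injection.
- 2% to 10% of patients are injected, and 5% to 20% of those sit at a threshold.
- True ACR20 rate of 50% to 70%.

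**Step 1: one joint alone.** With baseline count b and nothing else changed, apparent improvement is 1/b: 16.7% at b = 6, 10.0% at b = 10, 5.0% at b = 20. Reaching 20% needs b ≤ 5, which entry rules out.

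**Step 2: tipping a borderline patient.** Let f be the number of joints still swollen at follow-up, including the injected one.

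| Threshold | b | f | As written, 1 − (f−1)/b | Carried forward, 1 − f/b | Removed from both visits, 1 − (f−1)/(b−1) |
|---|---|---|---|---|---|
| 20% | 10 | 9 | 20.0%, met | 10.0%, not met | 11.1%, not met |
| 20% | 6 | 5 | 33.3%, met | 16.7%, not met | 20.0%, met |
| 50% | 6 | 4 | 50.0%, met | 33.3%, not met | 40.0%, not met |
| 70% | 10 | 4 | 70.0%, met | 60.0%, not met | 66.7%, not met |

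At the 20% threshold, each baseline from 6 to 20 has exactly one value of f at which the exclusion changes the result. Carrying the joint forward undoes all 15. Removing it from both visits undoes 12 and leaves 3 (b = 6, 11 and 16). Prorating by 66/65 undoes only 4 (b = 10, 15, 19 and 20).

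**Step 3: Boolean remission.** With two joints still swollen, one of them injected, the recorded count is 2 − 1 = 1 and the swollen criterion is met. No baseline enters this criterion, so removing the joint from baseline changes nothing.

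**Step 4: visits reached.** No timing limit is tied to Week 12, so an injection between baseline and Week 12 can leave the joint not done at that visit. For Week 24, the exclusion reaches back to 24 − 12 = Week 12, while the timing limit starts at 24 − 8 = Week 16. A joint injected between about Weeks 12 and 16 can therefore be not done at Week 24.

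**Step 5: size.** The upper bound on inflation of an arm's ACR20 rate is the share injected times the share at a threshold:
- low: 2% × 5% = 0.1 points;
- high: 10% × 20% = 2.0 points.

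For scale, the 95% half-width for a difference is 1.96 × √(2p(1−p)/130): 12.2 points at p = 0.5 and 11.1 at p = 0.7.

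**The case against.** The strongest reply is that this is a gap in specification with little practical weight. Much of that stands. Injections are discouraged and limited to one joint per 24-week period. ACR20 is descriptive, with no margin or test, and the primary endpoint is hypersensitivity events. ACR20 also needs 20% in the tender count and in three of five other measures, so meeting the swollen component is not a response. The rule is introduced for ACR measures, and the 28-joint section has no counterpart. If it is carried over, one swollen joint moves CDAI or SDAI by 1 point. It moves DAS28 by 0.28 × (√6 − √5) = 0.06 at a count of 6, against the 0.6 that Protocol 5.2.3.3 treats as possibly meaningful.

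A reader might infer four stronger things that the documents do not support.
- That the plan states the joint stays in baseline. It does not; this is the default reading of a fixed baseline with numerical improvement.
- That the exclusion alone produces response. Step 1 rules that out for one joint. Two joints excluded together would need the 24-week period to mean fixed blocks, which the documents do not say.
- That the direction is always upward. A joint not swollen at baseline creates no mismatch with the baseline count. Also, "Intra-articular corticosteroids are not permitted within 6 weeks prior to baseline", so an earlier injection is allowed. If the 12-week exclusion is applied to such a joint, it could be missing at baseline and return later, which lowers apparent improvement.
- That the arms are pulled together. The rule is blind to arm, and nothing in the documents shows unequal injection use.

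It may also be objected that the identity of the injected joint is not collected, since Protocol 6.4 lists only drug details. That fails: Protocol 7.3.1.1 requires the joint itself to be recorded as not done.

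**Conclusion.** The concern holds in a limited form. The exclusion is written into the protocol, and no text available in either document says how the excluded joint enters a comparison with baseline. Programmed on the default reading, an injected joint that failed to respond is scored as improved. This can change the result only for patients already at a threshold. The bound of 0.1 to 2.0 points rests on assumed injection use and is well inside the uncertainty of the ACR20 difference. A difference between arms would need unequal injection use as well. SAP Appendix I, which details the per-protocol exclusions, is not in the available text, so handling of injected patients in that set cannot be judged. The change should be made because it is cheap and removes an arbitrary choice, not because the trial's conclusions are likely to turn on it.

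**What to change.** Add to SAP 15.2, before database lock: for the 12 weeks after an intra-articular injection, the injected joint takes its last pre-injection tender and swollen status. Apply this in the 66-joint swollen count, the 68-joint tender count and the 28-joint counts, for all joint-count efficacy endpoints.

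Do not offer removal of the joint from baseline as an equivalent option. It leaves absolute-count measures such as Boolean remission uncorrected and does not reverse the tip at baselines of 6, 11 and 16.

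Two reconciliations go with this:
- The joint form in Protocol Appendix D has codes 0, 1 and 9 (not applicable) but none for not done. State how a not-done joint is coded and told apart from one excluded since screening.
- Protocol 5.2 (the Week 24 joint-count rule), 6.4.2 (injection timing) and 7.3.1.1 (the 12-week exclusion) must be reconciled on how an injected joint enters the Week 24 rule. What that clinical rule should be is for the sponsor to decide.

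The cost is one derivation rule and a coding note. Joint status is already recorded joint by joint at each assessment, so no new data are needed.
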